4.5.6 Patient-Reported and Clinician-Reported Outcomes Assessed during Site Visits

Patients will complete patient-reported outcome (PRO) assessments to capture their direct experience and potentially characterize the clinical impact of MSTT1041A. The questionnaires, translated into the local language as required, will be completed in their entirety at specified timepoints during the study. To ensure instrument validity and that data standards meet health authority requirements, questionnaires will be self-administered before the patient receives any information on disease status, prior to the performance of other site-visit assessments and procedures and prior to the administration of study treatment.

Clinician-reported outcome (ClinRO) data will be collected via a self-administered questionnaire to allow clinicians to report their impression of each patient's change in asthma symptoms. Clinicians will complete the questionnaire after they have examined patients and performed other study-related health assessments.

Patients will use an electronic device to complete their PRO assessments. The PRO questionnaires will be pre-programmed on electronic devices so that the appropriate questionnaires will be administered in order at specific site visits as specified in the schedule of activities (see [Appendix 1](#)). The PRO assessments should take between approximately 5 and 25 minutes to complete (shorter at most visits, longer at the randomization visit, Week 26, and Week 54 visit). The electronic device and/or instructions for completing the questionnaires electronically will be provided by the investigator staff. The data will be transmitted to a centralized database maintained by the electronic device vendor. The data will be available for access by appropriate study personnel.

4.5.6.1 Asthma Control Questionnaire

Asthma control, as measured by the Asthma Control Questionnaire (ACQ) (Juniper et al. 1999b), will be assessed by asking patients to recall their experience with asthma during the previous week. The full ACQ consists of seven questions: five questions related to symptoms (i.e., nighttime awakening, asthma symptoms upon awakening in the morning, activity limitation, shortness of breath, and wheezing frequency), one question about use of short-acting rescue therapy, and one question about FEV₁ (to be completed by site staff). The items are scored on a scale ranging from 0 (totally controlled) to 6 (extremely poorly controlled). The items are equally weighted. The ACQ can be scored three ways: 1) the mean of the five symptom-related items (ACQ-5); 2) the mean of the five symptom-related items plus the short-acting rescue use item (ACQ-6); or 3) the mean of all 7 items (ACQ). The ACQ has strong measurement properties for use in both clinical practice and clinical trials. The ACQ-5 is part of the eligibility criteria and will be administered at the screening and run-in visits. The ACQ will be administered at the randomization visit, Week 26, and Week 54.

A copy of the ACQ is provided in [Appendix 5](#).

4.5.6.2 Standardized Asthma Quality of Life Questionnaire

The Standardized Asthma Quality of Life Questionnaire (AQLQ[S]) will be used to assess the patients' asthma-specific health-related quality of life (Juniper et al. 1999a). The 32-item questionnaire contains four domains: activity limitations, symptoms, emotional function, and environmental stimuli. The AQLQ(S) has a recall specification of 2 weeks. Items are scored on a 7-point scale ranging from 1 (severe impairment) to 7 (no impairment). A copy of the AQLQ(S) is provided in [Appendix 6](#). The AQLQ(S) will be administered at the randomization visit, Week 26, and Week 54.

4.5.6.3 St. George's Respiratory Questionnaire

The St. George's Respiratory Questionnaire (SGRQ) is a 50-item respiratory-specific quality-of-life questionnaire initially developed and validated for use in COPD (Jones et al. 1992). It includes questions that assess the impact of disease on symptoms, activity, and functionality. The symptom scale assesses the severity of respiratory symptoms, the activity scale examines impairment in patient activity as a result of respiratory

symptoms, and the impact scale evaluates effects of respiratory symptoms on overall function and well-being. Each scale is scored from 0 to 100, and a total score represents the weighted average of these three subscores. Items are assessed on various response scales, including a 5-point Likert scale and a true/false scale. The SGRQ has a recall period of the past 4 weeks. Recently, the SGRQ has been applied more broadly to assess patients with airflow limitation due to causes other than COPD, including asthma (Ortega et al. 2014). The SGRQ will be administered in the clinic at the randomization visit, Week 26, and Week 54. A copy of the SGRQ is provided in [Appendix 7](#).

4.5.6.4 Clinician Global Impression of Change

The Clinician Global Impression of Change (CGIC) is a single-item assessment of the clinician's impression of a patient's change in asthma symptoms since beginning the 52-week double-blind treatment period (Visit 3). Change in asthma symptoms is rated on a 7-point scale ranging from "very much worse" to "very much improved." The CGIC is completed by the clinician and takes less than 1 minute to complete. The CGIC will be completed at Weeks 26 and 54. A copy of the CGIC is provided in [Appendix 8](#).

4.5.6.5 Patient Global Impression of Change

The Patient Global Impression of Change (PGIC) is a single-item assessment of the patient's impression of his or her change in asthma symptoms since beginning the 52-week double-blind treatment period. Change in asthma symptoms is rated on a 7-point scale ranging from "very much worse" to "very much improved." The PGIC will be administered in the clinic at Weeks 26 and 54. A copy of the PGIC is provided in [Appendix 9](#).

4.5.6.6 EuroQol 5-Dimension Questionnaire

The EuroQol 5-Dimension Questionnaire, 5-level version (EQ-5D-5L), is a self-reported health status questionnaire that consists of six questions used to calculate a health utility score for use in health economic analysis (EuroQol Group 1990; Brooks 1996; Herdman et al. 2011; Janssen et al. 2013). There are two components to the EQ-5D-5L: a five-item health state profile that assesses mobility, self-care, usual activities, pain/discomfort, and anxiety/depression, as well as a visual analogue scale that measures health state. Published weighting systems allow for creation of a single summary score. Overall scores range from 0 to 1, with low scores representing a higher level of dysfunction. The EQ-5D-5L will be utilized in this study for economic modeling. The EQ-5D-5L will be administered in the clinic at the randomization visit and at the Week 54 visit. A copy of the EQ-5D-5L is provided in [Appendix 10](#).

4.5.7 Physical Examinations

A complete physical examination should be performed at screening and should include an evaluation of the head, eyes, ears, nose, and throat, and the cardiovascular, dermatological, musculoskeletal, respiratory, gastrointestinal, and neurological systems.

Any abnormality identified at screening should be recorded on the General Medical History and Baseline Conditions eCRF.

At subsequent visits (or as clinically indicated), limited, symptom-directed physical examinations should be performed. Changes from abnormalities recorded at screening should be recorded in patient notes. New or worsened clinically significant abnormalities should be recorded as adverse events on the Adverse Event eCRF.

4.5.8 **Vital Signs**

Vital signs will include measurements of temperature, respiratory rate, pulse rate, and systolic and diastolic blood pressure. Patients should *ideally* be in a seated position in a rested and calm state for at least 5 minutes before taking vital sign measurements.

4.5.9 **Electrocardiograms**

Triplicate ECG recordings will be obtained at specified visits, as outlined in the schedule of activities (see [Appendix 1](#)), and may be obtained at unscheduled visits as indicated. Three interpretable ECG recordings (e.g., without artifacts) *should* be obtained at each visit, typically within 15 minutes. The average of the three readings will be used to determine ECG intervals (e.g., PR, QRS, QT).

All ECG recordings must be performed using a standard high-quality, high-fidelity digital electrocardiograph machine equipped with computer-based interval measurements. Lead placement should be as consistent as possible. ECG recordings must be performed after the patient has been resting in a supine position for at least 10 minutes. All ECGs are to be obtained prior to other procedures scheduled at that same time (e.g., blood draws). Circumstances that may induce changes in heart rate, including environmental distractions (e.g., television, radio, conversation) should be avoided during the pre-ECG resting period and during ECG recording.

For safety monitoring purposes, the investigator must review, sign, and date all ECG tracings. Paper copies of ECG tracings will be kept as part of the patient's permanent study file at the site. Digital recordings will be stored at a central ECG laboratory. The following should be recorded: heart rate, RR interval, QRS interval, PR duration, uncorrected QT interval, and QTcF based on the machine readings of the individual ECG tracings. Any morphologic waveform changes or other ECG abnormalities must be documented. If considered appropriate by the Sponsor, ECGs may be analyzed retrospectively at a central laboratory.

If at a particular postdose timepoint, the mean QTcF is >500 ms and/or > 60 ms longer than the value at the randomization visit, another ECG must be recorded, ideally within the next 5 minutes, and ECG monitoring should continue until QTcF has stabilized on two successive ECGs. The same procedure (i.e., triplicate ECGs) should be repeated approximately 30 minutes after QTcF has stabilized on two successive ECGs of the first measurement. The Medical Monitor should be notified. Standard-of-care

treatment may be instituted per the discretion of the investigator. If a PK sample is not scheduled for that timepoint, an unscheduled PK sample should be obtained. A decision on study drug discontinuation should be made, as described in Section 5.1.2.3. The investigator should also evaluate the patient for potential concurrent risk factors (e.g., electrolyte abnormalities, co-medications known to prolong the QT interval, severe bradycardia).

4.5.10 Chest X-Rays

Patients with a positive PPD (without a history of Bacillus Calmette-Guérin vaccination) or a positive or indeterminate QFT will require a chest X-ray to review for evidence of active TB, including posteroanterior and lateral views, unless a chest X-ray has been performed within 3 months prior to screening and the report is available for review. A chest computed tomography (CT) scan may substitute for a chest X-ray. Chest X-rays should only be performed if patients first meet all other study eligibility criteria. All imaging should be read by a radiologist or per local requirements.

4.5.11 Asthma Exacerbations

At each study visit, the investigator will ask directed questions to assess whether the patient experienced any asthma exacerbations as defined in Appendix 12 since the last study visit.

Given that asthma exacerbations are the primary endpoint in this study, a dedicated eCRF will be used to record information regarding asthma exacerbation events. An asthma exacerbation must also be reported as an adverse event (or serious adverse event as applicable) (refer to Section 5 for more details). Sites should record all medications used for treatment of the asthma exacerbation in the appropriate eCRF.

Patients who experience symptoms consistent with an asthma exacerbation should be asked to come to the clinic for an unscheduled visit if possible. Patients will be asked to bring from home a urine sample collected at symptom onset. Additional evaluations will be performed as outlined in the schedule of activities (Appendix 1).

4.5.12 Spirometry

Spirometry, including the procedure for bronchodilator testing, will be conducted as per the study pulmonary function testing manual, which is based on the American Thoracic Society/European Respiratory Society (ATS/ERS) Consensus Statement "Standardisation of Spirometry" (Miller et al. 2005). The manual will include information on equipment, procedures, patient instructions, and precautions. Standardized ATS- and ERS-compliant spirometric equipment, including software, will be dispensed to all sites. Training on equipment use, system calibration, and data storage and transfer will be provided.

4.5.12.1 Pre-Bronchodilator Spirometry

Pre-bronchodilator spirometry evaluations should be performed in the morning, before use of bronchodilators. Asthma therapies that may affect spirometry must be withheld until pre-bronchodilator spirometry measurements are completed. Patients must be made aware that bronchodilator use is prohibited within a specified window prior to each clinic visit, with the exception of the screening visit or an unscheduled visit, as follows:

- Twice-daily LABA and twice-daily LAMA: prohibited within 12 hours prior to spirometry
- Once-daily LABA and once-daily LAMA: prohibited within 24 hours prior to spirometry
- SABA or SAMA: prohibited within 4 hours prior to spirometry

With the exception of an unscheduled visit, a patient's visit must be rescheduled if the patient arrives for a study visit having used a bronchodilator within the time window defined above for each medication. To accommodate the rescheduled visit, the usual visit window specified in the schedule of activities (see [Appendix 1](#)) may be extended to ± 4 days for Week 4 or ± 6 days for Week 6–54.

For safety reasons, consideration should be given to omitting spirometry if a patient is having an acute asthma exacerbation event at the time of the scheduled study visit.

Spirometric assessments will include FEV₁, forced vital capacity (FVC), percentage of predicted values for FEV₁ and FVC, FEV₁ to FVC ratio, and average expiratory flow during the middle portion of the expiration (FEF_{25–75}). The percentage of predicted values for FEV₁ and FVC will be derived from the third National and Nutrition Examinations Survey (Hankinson et al. 1999). Each test procedure requires that three valid spirometry maneuvers be performed within 1 hour. The highest FEV₁ and FVC values from the set of three accepted maneuvers will be recorded. Other parameters will be taken from the accepted maneuver with the highest sum of FEV₁ and FVC. A hard-copy report of the spirometry results will be maintained in the patient's medical record.

4.5.12.2 Post-Bronchodilator Spirometry

At screening, post-bronchodilator FEV₁ measurements will be recorded 15 to 45 minutes after bronchodilator use. Up to 8 puffs of SABA or nebulized equivalent (e.g., 2 treatments with 2.5 mg albuterol/salbutamol) should be administered in a step-wise fashion, as follows:

- Administer 4 puffs, followed by spirometry.
- If bronchodilator reversibility improvement criteria are not met, administer 2 to 4 additional puffs, followed by spirometry.

4.5.13 Fractional Exhaled Nitric Oxide

FeNO is a volatile marker of airway inflammation and has been demonstrated to decrease with ICS treatment. Standard nitric oxide machines will be provided to the site and should be used for all study-related FeNO measurements. Patients will be asked to refrain from nitrate-rich foods (such as processed meats [bacon, lunchmeat, hot dogs, sausage], spinach, green beans, broccoli, and cauliflower) for at least 8 hours prior to the study visit and to avoid food or drink for at least 1 hour prior to completing at least three (and up to six) separate measurements according to ATS guidelines (training and guidance to be provided separately) (American Thoracic Society 2005).

4.5.14 Laboratory, Biomarker, and Other Biological Samples

Samples for the following laboratory tests will be sent to the study site's local laboratory for analysis or analyzed at point of care:

- Urine pregnancy test for all women of childbearing potential
Urine pregnancy tests will be performed at the site prior to each administration of study drug and at other specified visits after treatment discontinuation. If a local urine pregnancy test shows a positive result, study drug will not be administered that day. The result must be confirmed by a serum pregnancy test (conducted by the central laboratory). Refer to Section 5.4.3.1 for management of a patient with a confirmed pregnancy.
- TB tests: PPD or QFT (QFT may be conducted by the central laboratory, per Sponsor agreement with site)
- Serum theophylline levels (only for patients taking theophylline, per standard of care)

Samples for the following laboratory tests will be sent to one or several central laboratories for analysis:

- Serum pregnancy test for all women of childbearing potential
Serum pregnancy tests will be performed at screening and at subsequent visits if a local urine pregnancy test is positive. Study drug will not be administered if a patient has a positive pregnancy test. Refer to Section 5.4.3.1 for management of a patient with a confirmed pregnancy.
- Hematology: WBC count, RBC count, RBC morphology, hemoglobin, hematocrit, platelet count, ANC, differential count (neutrophils, eosinophils, basophils, monocytes, lymphocytes, other cells)
- Chemistry panel (serum or plasma): sodium, potassium, chloride, bicarbonate, glucose, BUN or urea, creatinine, total protein, albumin, phosphorus, calcium, magnesium, total and direct bilirubin, alkaline phosphatase, ALT, AST, uric acid, LDH
- Fasting lipids: cholesterol, LDL cholesterol, HDL cholesterol, triglycerides
- Fasting glucose and HbA_{1c}

- Viral serology: hepatitis B surface antibody (HBsAb), hepatitis B surface antigen (HBsAg), total hepatitis B core antibody (HBcAb), hepatitis C virus (HCV) antibody
 - HCV RNA
 - HBV DNA

Note: For patients with eligible HBV DNA test result at screening, the HBV DNA test will be repeated at Week 14 and Week 38. If the HBV DNA test value is ≥ 20 IU/mL at Week 14 and Week 38, the medical monitor should be notified.

- Urinalysis: pH, specific gravity, glucose, protein, ketones, blood, RBCs, WBCs, epithelial cells, bacteria, bilirubin, and leukocyte esterase

The following samples will be sent to the Sponsor or a designee for analysis:

- Serum samples for MSTT1041A PK analysis
- Serum samples for immunogenicity analysis
- Serum total and specific IgE test
- Blood RNA, blood DNA, serum, plasma, and urine samples for exploratory research on biomarkers (see [Table 3](#))

Exploratory biomarker research may include, but will not be limited to, the biomarkers listed in [Table 3](#).

Table 3 Proposed Biomarkers for Exploratory Research

Sample Type	Timing	Proposed Biomarkers
Plasma	Prior to active treatment and subsequent timepoints during treatment	• Inflammatory chemokines
Serum	Prior to active treatment and subsequent timepoints during treatment	• IgE, periostin, CCL13, CCL17, sST2, IL-13, IL-33, IL-5, amphiregulin, LIGHT
Breath	Prior to active treatment and subsequent timepoints during treatment	• FeNO
Urine	Prior to active treatment and subsequent timepoints during treatment	• Inflammatory lipids
Blood	Prior to active treatment and subsequent timepoints during treatment	• Eosinophils, neutrophils
RNA extracted from blood	Prior to active treatment and subsequent timepoints during treatment	• Inflammatory gene signature
DNA extracted from blood	Prior to active treatment	• IL1RL1 , IL-33 , GLCC1

For sampling procedures, storage conditions, and shipment instructions, see the laboratory manual.

Unless the patient gives specific consent for his or her leftover samples to be stored for optional exploratory research (see Section 4.5.15), biological samples will be destroyed when the final Clinical Study Report has been completed, with the following exceptions:

- Serum samples collected for PK analysis or immunogenicity analysis will be destroyed no later than 5 years after the final Clinical Study Report has been completed.
- Blood RNA, blood DNA, serum, plasma, and urine samples collected for biomarker analysis will be destroyed no later than 10 years after the final Clinical Study Report has been completed.

When a patient withdraws from the study, samples collected prior to the date of withdrawal may still be analyzed, unless the patient specifically requests that the samples be destroyed or local laws require destruction of the samples.

Data arising from sample analysis, including data on germline mutations, will be subject to the confidentiality standards described in Section 8.4.

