- Documented history of a completed course of adequate prophylaxis (completed treatment for latent TB per the treatment options as stated in the WHO guideline) prior to screening
- No known exposure to a case of active TB after most recent prophylaxis
- No evidence of active TB on chest radiograph within 3 months prior to screening

- Positive hepatitis C virus (HCV) antibody test result at screening, unless the patient has undetectable HCV RNA test value of < 15 IU/mL (or undetectable) for > 6 months after completing a successful course of HCV anti-viral treatment and a HCV RNA test value < 15 IU/mL at screening OR has a known history of HCV antibody positivity with history of undetectable HCV RNA for > 6 months and a HCV RNA test value < 15 IU/mL at screening in the absence of history of HCV anti-viral treatment.
- Unacceptable test results for hepatitis B surface antigen (HBsAg), hepatitis B surface antibody (HBsAb), and hepatitis B core antibody total (HBcAb) at screening.
- If HBsAg testing is positive, patient is not eligible. For patients with a negative HBsAg testing, following criteria apply:
 - If HBsAb testing is negative and HBcAb is positive, patient is not eligible
 - If HBsAb testing is positive and HBcAb is negative, patient is eligible
 - If HBsAb testing is negative and HBcAb is negative, patient is eligible
 - If HBsAb testing is positive and HBcAb is positive, patient must undergo further testing for hepatitis B virus DNA (HBV DNA):
 - Patient is not eligible, if HBV DNA test value is ≥ 20 IU/mL or test cannot be performed
 - Patient is eligible, if HBV DNA test value is < 20 IU/mL

- History of anaphylaxis to any biologic therapy for any indication
- History of documented immune complex disease (Type III hypersensitivity reactions) to monoclonal antibody administration
- History of any known immunodeficiency disorder, including but not limited to HIV infection
- Active malignancy, including cutaneous basal or squamous cell carcinoma or melanoma
- History of malignancy within 5 years prior to screening, except for cases specifically involving cutaneous basal or squamous cell carcinoma (non-melanoma skin cancers), cervical carcinoma in situ, or breast ductal carcinoma in situ that have been treated and considered cured
- Planned surgical intervention during the course of the study
- Asthma exacerbation as defined in [Appendix 12](#) within 4 weeks prior to screening

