5.1.1.4 Infection

The intended mechanism of action of MSTT1041A suggests inhibitory effects on immune responses mediated by Th2 cells, leading to the possibility of a decrease in the protective response to infection. MSTT1041A may have additional, unanticipated immune-mediated side effects.

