5.1.2.3 Management of Increases in QT Interval

Study drug should be discontinued in patients who develop any of the following, unless there is a clear alternative cause for the changes:

- Sustained (at least two ECG measurements >30 minutes apart) QTcF that is >500 ms and >60 ms longer than the baseline value
- Sustained absolute QTcF that is >515 ms
- An episode of torsades de pointes or a new ECG finding of clinical concern

Of note, if there is a new intraventricular conduction block, the increase in QRS complex duration should be subtracted from the QTcF change, because this represents an

increase in QTcF unrelated to alterations in repolarization. Also of note, it is not uncommon to record arrhythmias such as non-sustained ventricular tachycardia, supraventricular tachycardia, pauses, or atrial fibrillation in healthy volunteers receiving placebo during periods of extended ECG monitoring. Therefore, it is critical that expert cardiology advice be sought to confirm any ECG changes and to ascertain the likelihood of a drug-induced arrhythmia versus the background occurrence of this arrhythmia. In such a situation, saving all available ECG data is highly suggested.

Management of patients with sustained QTcF prolongation should include close monitoring, with ECGs repeated at least hourly until two successive ECGs show resolution of the findings, correction of any electrolyte abnormalities, and possible discontinuation of other concomitant medications that are known to prolong the QT interval. Consultation with a cardiologist or electrophysiologist is recommended, to help in the management of such patients.

In rare circumstances, it may be acceptable to resume study drug, provided that any ECG abnormalities have resolved and the patient is appropriately monitored. Clinical judgment should be applied.

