9.4 ADMINISTRATIVE STRUCTURE

Genentech, a member of the Roche group, is the Sponsor of this study. A CRO may provide clinical operations oversight, including, but not limited to, project management, medical monitoring, site management, data quality support, safety reporting, and regulatory activities as specified in the study management plans. Genentech will provide CRO oversight, develop the database and randomization scheme, and conduct statistical programming and analysis. An IDMC will provide safety monitoring for the study in addition to the ongoing review of safety by the Medical Monitor and safety scientist. EDC will be utilized for this study. An IxRS will be used to assign patient numbers, randomize patients into the study through use of a dynamic hierarchical algorithm, and manage site drug supply. A central laboratory will be used for sample management and storage until shipment to specialty laboratories or Genentech for analysis. Data reported by patients regarding their asthma symptoms and medication use will be captured electronically via handheld mobile devices. Patients will be randomized through use of an IxRS.

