Appendix 1 Schedule of Activities (cont.)

- ^u Hematology includes WBC count, RBC count, RBC morphology, hemoglobin, hematocrit, platelet count, ANC, differential count (neutrophils, eosinophils, basophils, monocytes, lymphocytes, other cells).
- ^v Chemistry panel (serum or plasma) includes sodium, potassium, chloride, bicarbonate, glucose, BUN or urea, creatinine, magnesium, total protein, albumin, phosphorus, calcium, total and direct bilirubin, alkaline phosphatase, ALT, AST, uric acid, LDH.
- ^w Lipid panel includes cholesterol, LDL cholesterol, HDL cholesterol, triglycerides.
- ^x If patient has not fasted for 8 hours, patient must return to site for fasting blood draw. Patients will be given 2 weeks to return for a fasting blood draw.
- ^y Includes hepatitis B surface antibody, hepatitis B surface antigen, total hepatitis B core antibody, and hepatitis C virus antibody.
- ^z Measurement of HCV RNA with use of a quantitative PCR assay is only required when the patient was tested positive for HCV antibody at screening and has a known history of HCV antibody positivity with past documentation of undetectable HCV RNA, either with or without history of anti-viral treatment. Patients with newly diagnosed HCV antibody positivity are not eligible for this study and, therefore, do not require measurement of HCV RNA.
- ^{aa} For patients with a HbsAg negative, HbsAb positive, and HbcAb positive test result at screening only, as described in Section 4.1.2.1. Patients with a HBV DNA test value ≥ 20 IU/mL at screening are not eligible. Patients with a HBV DNA test value < 20 IU/mL at screening must undergo re-testing of HBV DNA at Week 14 and Week 38. If the HBV DNA test value at Week 14 and Week 38 is ≥ 20 IU/mL, the medical monitor should be notified.
- ^{bb} Urinalysis includes pH, specific gravity, glucose, protein, ketones, blood, RBCs, WBCs, epithelial cells, bacteria, bilirubin, and leukocyte esterase.
- ^{cc} PK samples to be collected prior to study drug administration.
- ^{dd} Patients will be supplied with urine collection cups to allow for urine sample collection at home prior to coming to the clinic for an unscheduled visit. If the patient did not bring in a urine sample collected at home, the patient will be asked to provide the urine sample at the visit.
- ^{ee} If the DNA is not collected at the randomization visit for any reason, it may be collected at any later timepoint.

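### The HBV DNA notification rule joins its two retest visits with 'and', so taken literally one positive retest does not trigger it

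*Protocol*

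**What the plan says.** At screening, Protocol Section 4.1.2.1 requires an HBV DNA test in patients who are HBsAg negative with both HBsAb and HBcAb positive. One result decides eligibility: "Patient is not eligible, if HBV DNA test value is" 20 IU/mL or above.

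Patients admitted with a value below 20 IU/mL are followed on treatment. Section 4.5.14 says that "the HBV DNA test will be repeated at Week 14 and Week 38". The next sentence gives the action: with a value of 20 IU/mL or more "at Week 14 and Week 38, the medical monitor should be notified".

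Appendix 1 footnote aa states the same rule in slightly different order, opening with "If the HBV DNA test value at Week 14 and Week 38 is" and ending in the same notification. No other section restates the rule, and neither version uses 'or' or 'either'.

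**The concern.** A retest schedule properly joins its visits with 'and'. A trigger does not, if each result is meant to count separately. Here the schedule's wording has been carried into the trigger, and the literal condition becomes a positive result at both visits.

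The patients concerned have serological evidence of hepatitis B exposure and receive a drug for which Section 5.1.1.4 lists, as a potential risk, "inhibitory effects on immune responses mediated by Th2 cells, leading to the possibility of a decrease in the protective response to infection". The two retests are the only scheduled HBV DNA checks on treatment, and telling the medical monitor is the only consequence stated specifically for them. A site that applied the sentence literally could hold a positive Week 14 result without passing it on, or never pass on a first positive at Week 38.

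**Working it through.** There is no stated figure to reproduce. The check is to work through the rule under each reading, then ask whether other provisions fill any gap.

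**Inputs.** Retests at Weeks 14 and 38, threshold 20 IU/mL (Section 4.5.14; Appendix 1 footnote aa). Dosing at Week 2, Week 6 and every 4 weeks to Week 50 (Section 3.1.1).

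**When the rule operates.** These are logical cases; the documents give no rates.

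| Week 14 / Week 38 result | Either retest counts | Both retests needed |
|---|---|---|
| positive / positive | Week 14 | Week 38 |
| positive / negative | Week 14 | never |
| negative / positive | Week 38 | never |
| negative / negative | never | never |

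- Delay in the first row: 38 − 14 = 24 weeks.
- Scheduled doses between those two visits: Weeks 18, 22, 26, 30 and 34, that is, five. This describes the interval. It is not a count of doses that notification would prevent, because the rule attaches no dosing action.

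**Whether other provisions require the medical monitor to be told of one positive result.**

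| Protocol section | What it provides | Requires it? |
|---|---|---|
| 3.1.2 | iDMC reviews laboratory data about every 3 months | No; no HBV DNA trigger |
| 4.6.2 | Investigator or Sponsor may stop study drug for a condition that threatens safety | No; judgment |
| 5.1.2.1 | Suspension for reasons other than toxicity needs Medical Monitor approval | Only if the investigator decides to suspend |
| 5.1.2.2, Table 4 | Action on ALT/AST, total bilirubin and alkaline phosphatase | No; HBV DNA is not listed |
| 5.2.2 | An event judged medically significant is serious and goes to the Sponsor within 24 hours | No; judgment |
| 5.2.3 | Special-interest events: Hy's law cases and suspected contamination of study drug | No |
| 5.3.5.5 | Investigator reviews all laboratory findings; adverse event if symptomatic, acted on or judged significant | No; an isolated symptom-free result does not qualify automatically |
| 7.1 | Central laboratory data go directly to the Sponsor | No; receipt is not notification of the medical monitor |
| 9.4 | Ongoing safety review by the Medical Monitor | No; no HBV DNA trigger |

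The chemistry panel, which feeds Table 4, is drawn at 14 visits after randomization: Weeks 4, 6, 10, 14, 18, 22, 26, 30, 34, 38, 42, 46, 50 and 54. Liver injury would therefore be looked for often. A positive HBV DNA result with normal liver tests would not meet any Table 4 criterion.

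**The case against.** The best reply is that no careful reader would require two positives. The preceding sentence in Section 4.5.14 uses the same phrase for two separate tests, footnote aa speaks of a single value, and one value at the threshold excludes a patient at screening. Elsewhere the protocol writes 'and' between visits to mean each visit, as with the global impression scales at Weeks 26 and 54 (Sections 4.5.6.4 and 4.5.6.5). This stands as evidence of intent: the per-test meaning is probably what the sponsor had in mind, and under it nothing goes wrong. It does not change what the sentence literally requires. The visit examples are schedules rather than triggers.

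A reader might infer a deliberate two-result rule from the QTc provisions. Section 4.5.9 acts when "the mean QTcF is >500 ms and/or > 60 ms longer than the value at the randomization visit", and Section 5.1.2.3 discontinues for a sustained "QTcF that is >500 ms and >60 ms longer than the baseline value", so the protocol appears to separate 'and/or' from 'and'. The documents do not support that inference. Those rules join two different criteria for QTcF; the HBV DNA rule has one criterion measured at two visits.

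A reader might also infer that a single positive has no consequence at all. That is too strong. An investigator who judged the result significant would report it, and one who suspended dosing for a reason other than toxicity would need the Medical Monitor's approval. Section 9.4 also places the iDMC's monitoring "in addition to the ongoing review of safety by the Medical Monitor and safety scientist". These routes narrow the gap. They do not close it, because each rests on judgment or does not name HBV DNA.

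**Conclusion.** The point holds as a minor wording fault in an operative safety rule. Read literally, the rule cannot operate before Week 38. It tells the medical monitor of a Week 14 positive 24 weeks late when the second test is also positive, and misses any patient positive at only one retest. All of this is conditional on a site applying the literal wording; on the probably intended reading there is no effect.

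The practical reach cannot be sized. The documents do not say how many patients are retested, and under 1:1:1:1 allocation about one in four of them would be on placebo. Two further inferences should be avoided. The wording does not by itself keep anyone on drug, since notification has no stated dosing action. The protocol also does not name hepatitis B reactivation as a risk; Section 5.1.1.4 speaks only of infection in general. No endpoint, sample size, error rate or analysis is touched.

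**What to change.** In the notification sentence of Protocol Section 4.5.14, and in the matching sentence of Appendix 1 footnote aa, change 'and' to 'or' between the two visits. A value of 20 IU/mL or more at Week 14 or Week 38 then leads to notification. Leave the sentences that schedule the retests unchanged, since 'and' is correct there.

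The cost is one word in each of two places and at most a few extra notifications, with no change to visits, samples or analyses. SAP Section 2.2 records 502 patients as already randomized, so the practical route may be a clarification to sites, with the text corrected in any later protocol that reuses it.
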